8.6 Modifications to the protocol

This study will be conducted in compliance with the current version of the protocol. Any change to the protocol document or consent documentation that affects the scientific intent, study design, patient safety, or may affect a participant's willingness to continue participation in the study is considered an amendment, and therefore will be written and filed as an amendment to this protocol and/or consent documentation. All such amendments will be submitted to the HREC, for approval prior to becoming effective.

9 Safety monitoring and reporting

9.1 Data Monitoring and Ethics Committee (DMEC)

An independent DMEC has been set up to monitor recruitment and retention, protocol adherence (including adherence to treatment protocols) and patient safety. The DMEC will receive and review the progress and accruing data and provide advice on trial conduct to the TSC. The DMEC will also review the results of planned adaptive analyses to ensure that the pre-specified trial algorithm is being implemented as designed, and that the design remains appropriate from a scientific and ethical standpoint. The DMEC is also responsible for the review of unblinded safety data and will be notified of unexpected and serious adverse events and will make recommendations to the TSC of any action required.

9.2 Definitions

The following definitions have been adapted from Directive 2001/20/EC of the European Parliament (Clinical Trials Directive) and ICH-GCP guidelines (E6(R1), 1996).

Adverse Event

An Adverse Event (AE) is defined as: any untoward medical occurrence or effect in a patient participating in a trial.

Serious Adverse Event

An adverse event is defined as serious if it:

- Results in death
- Is life-threatening
- Requires in-patient hospitalisation or prolongation of existing hospitalisation
- Results in persistent or significant disability/incapacity
- Is a congenital anomaly/birth defect.

"Life-threatening" refers to an event in which the subject was at risk of death at the time of the event. It does not refer to an event that hypothetically might have caused death if it were more severe.

"Hospitalisation" refers to inpatient admission, regardless of length of stay. This includes admission for continued observation. Any admission for pre-existing conditions that have not worsened, or elective procedures, do not constitute an SAE. Important adverse events that are not immediately life-threatening, do not result in death or hospitalisation but may jeopardise the subject or require intervention to prevent one or any of the other outcomes listed in the definition above should also be considered as serious.

9.3 Assessment

The site PI, or other medically qualified investigator as listed on the Delegation Log, should make an assessment of the severity, relatedness and expectedness, categorised as follows:

9.3.1 Severity

- None: indicates no event or complication
- Mild: complications result in only temporary harm and do not require clinical treatment
- Moderate: complications require clinical treatment but do not result in prolongation of hospital stay. Does not usually result in permanent harm and where this does occur the harm does not cause functional limitations to the patient
- Severe: complications require clinical treatment and results in prolongation of hospital stay and/or permanent functional limitation
- Life-threatening: complication that may lead to death
- Fatal: where the participant died as a direct result of the complication/adverse event

An event assessed as 'Severe', 'Life-threatening' or 'Fatal' will be considered a Serious Adverse Event (SAE).

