9.3.3 Expectedness

- Expected: the event is a pre-defined expected SAE event for this trial.
- Unexpected: the event is not a pre-defined expected SAE event for this trial

Pre-defined expected SAEs for T4P that could be observed in participants up to ICU discharge following randomisation are:

- Major and fatal bleeds classified according to the HEME bleeding score
- Serious transfusion related adverse reactions which relate to the administration of the platelet transfusion

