On receipt of an SAE report, a member of the central (international) coordinating centre will first evaluate the report for completeness and internal consistency. Then, a clinical member of the central T4P Trial Management Group will evaluate the event for severity, relatedness and expectedness and liaise with the Australian Trial Management Group to determine whether the case qualifies for reporting to the (Australian) HREC and any further actions required, in accordance with local jurisdictional requirements and policy directives.

All other adverse events that occur between randomisation and 90 days post-randomisation (or ICU discharge, if sooner) must be recorded in the participant's medical notes.

The coordinating (international) centre will provide safety information to the DMEC on a basis deemed appropriate by the DMEC.

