12.3 Data variables collected

- 1. Screening
 - Patient identifier(s)
 - Inclusion and exclusion criteria
 - Reason for non-enrolment
- 2. Baseline (immediately prior to randomisation)
 - Baseline demographics
 - Severity of illness
 - Risk factors
- 3. Intervention
 - Data to monitor adherence with the protocol and randomised platelet transfusion threshold
 - Data on procedures undertaken, response to bleeding episodes and co-interventions
- 4. Outcome data
 - Secondary outcomes of ICU and acute hospital mortality
 - Organ support duration
 - Duration of ICU and acute hospital stay
 - Critical care costs from the index admission and any subsequent critical care readmissions
 - Date of deaths
 - Thromboembolism occurrence
 - Patient and PR contact details (to allow for questionnaire follow up)
 - Health care utilisation and quality of life outcomes up to one year post enrolment
- 5. Adverse event reporting
 - See section 9.

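### Sections 9.2 and 9.3.1 set different tests of a serious event and do not say which governs, so capture of transfusion reactions depends on the test a site applies

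*Protocol*

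**What the plan says.** Four parts of Protocol section 9 bear on whether an event is an SAE and reaches the trial team.

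- **9.2 Definitions** gives the usual list of serious outcomes and then widens it. Important events that "require intervention to prevent one or any of the other outcomes listed in the definition above should also be considered as serious". No condition on length of stay is attached. Life-threatening there means that the patient was at risk of death when the event happened; a merely hypothetical threat is excluded.
- **9.3.1 Severity** has its own scale. The middle grade reads: "Moderate: complications require clinical treatment but do not result in prolongation of hospital stay". The next grade up needs treatment together with a longer stay, a permanent functional limitation, or both. Life-threatening is here any complication that could lead to death. The section closes: "An event assessed as 'Severe', 'Life-threatening' or 'Fatal' will be considered a Serious Adverse Event (SAE".
- **9.3.3 Expectedness** lists two pre-defined expected SAEs: "Major and fatal bleeds classified according to the HEME bleeding score" and "Serious transfusion related adverse reactions which relate to the administration of the platelet transfusion".
- **9.4 Recording and reporting procedures** requires the pre-specified events to be reported for every randomised patient up to ICU discharge. It limits unexpected SAEs to those at least possibly caused by giving or withholding platelets. Other adverse events need only be written in the medical notes. Once a report arrives, "a clinical member of the central T4P Trial Management Group will evaluate the event for severity, relatedness and expectedness".

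Section 7.6 lists major and fatal HEME bleeds as a secondary outcome. It does not list transfusion reactions.

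**The concern.** A site investigator who follows section 9.3 in order grades severity first, and there meets a sentence that ties SAE status to the three highest grades. Read as a gate, it stops a treated event without a longer stay from being reported. Sections 9.2 and 9.3.3 may say that the same event must be reported.

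Bleeding is the harm that transfusion is meant to prevent, and transfusion reactions are a direct harm of giving it. Section 6.2.2 says that platelets have the highest reaction rate of any blood component. The trial is open label, so whoever grades an event knows the allocated threshold. If the rule for what counts can be read in two ways, the safety data that the DMEC sees by threshold may partly reflect how sites read section 9. All-cause mortality at 90 days, the primary clinical outcome, is not affected.

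**Working it through.** No formula applies, and the plan gives no figure to reproduce. The check is to take three kinds of event through each section.

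**A. A transfusion reaction, treated promptly, stay not prolonged, no lasting limitation.**
- 9.3.1: Moderate, so not among the grades named as SAE.
- 9.2: serious if the treatment averted one of the listed outcomes. This limb covers events that "do not result in death or hospitalisation but may jeopardise the subject or require intervention".
- 9.3.3: listed only if already serious, so this section does not settle the matter.
- 9.4: reported if the 9.2 test is used; otherwise medical notes only.
- Result: the two tests can disagree, and nothing breaks the tie.

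**B. A HEME major bleed, treated and controlled, stay not prolonged.**
- 9.3.1: could be graded Moderate, unless it is judged life-threatening.
- 9.3.3: an SAE by type, with no grade condition.
- 9.4: every occurrence is to be recorded and reported.
- Result: read together, 9.3.3 and 9.4 require the report. It is lost only if a site uses 9.3.1 as a gate ahead of 9.3.3. No sentence rules that reading out.

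**C. A complication that could lead to death, in a patient not at risk of death when it happened.**
- 9.3.1: life-threatening, hence an SAE.
- 9.2: not life-threatening, although it may still be serious under the wider limb.
- 9.5: a suspected unexpected serious adverse reaction is due within 7 calendar days if fatal or life-threatening, and within 15 otherwise. For such an event the choice of meaning also changes the reporting clock.

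**Direction.** For treated events without a longer stay, 9.3.1 is narrower than 9.2. For life-threatening, 9.3.1 is wider. The two differences pull in opposite directions, so the net effect on the number of reports cannot be signed.

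**Size.** It would require the share of events on which the tests disagree. The protocol gives no bleeding or reaction rate and does not reproduce the HEME criteria, so the share of major bleeds that could be graded Moderate lies anywhere from 0 to 100%. Assumed shares show how little can be said. With equal true rates, omitting 30% at high thresholds and 10% at low ones gives an apparent rate ratio (high to low) of (1 − 0.30)/(1 − 0.10) = 0.78. Swapping the shares gives (1 − 0.10)/(1 − 0.30) = 1.29. Neither pair comes from the documents, so neither ratio is an estimate for this trial.

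**The case against.** The strongest reply is that the rules add up and do not conflict. The closing sentence of 9.3.1 makes three grades sufficient for SAE status; it does not say that only those grades qualify. Section 9.2 says that further events are serious as well. Major and fatal HEME bleeds are named by type and must all be reported, so a site would have to disregard 9.3.3 and 9.4 to leave one out. This stands for bleeds. A reader might infer that sites following the protocol will omit bleeding endpoint events; the text does not support that.

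A reader might also infer that bleeding is captured only through SAE reports, because the outcome list in 12.3 has no bleeding item. That does not follow either. Item 3 of the same section collects "Data on procedures undertaken, response to bleeding episodes and co-interventions", section 13.2.2 has monitors review the outcome data for each participant, and the case report form is not shown and may hold HEME fields. Adding fields to 12.3 is therefore not part of this point.

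For reactions, 9.6 sends every suspected case to local transfusion reporting. That is a real safeguard for the patient, but the protocol does not say that those reports reach the trial database.

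The additive reading does not remove the inconsistency. It has to be inferred, it leaves two meanings of life-threatening in place, and it does not help a site that grades by 9.3.1 alone. Central evaluation under 9.4 sees only what has been submitted, so it cannot recover a report never made.

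**Conclusion.** The inconsistency is real and lies in a rule that sites will use. Sections 9.2 and 9.3.1 differ on what makes an event serious and on what life-threatening means, and neither is said to govern. The effect falls mainly on transfusion reactions, and on unexpected SAEs judged related to giving or withholding platelets, because both enter the reporting system only once called serious. Transfusion reactions are safety data here, not an outcome in 7.6. For major and fatal HEME bleeds the effect is limited to a risk of misreading.

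Neither the size nor the direction of any loss can be derived, so the documents do not support a claim that the bleeding curve is biased by a given amount. The conclusion assumes that no site manual or reporting form, none of which is shown, already settles which test applies. The passages should be reconciled because the defect is plain and cheap to remove, not because a large effect has been shown.

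**What to change.** 1. Reconcile 9.2 and 9.3.1 into one test of seriousness with one meaning of life-threatening, and use that meaning in 9.5. If the severity scale is kept, say whether it describes an event or decides whether it is an SAE.
2. State in 9.3.1 and 9.4 that the events pre-specified in 9.3.3 are reported irrespective of severity grade. For transfusion reactions, the word serious in 9.3.3 should point to the single test from step 1.
3. Have the central clinical reviewer, who already evaluates each SAE under 9.4, assign the HEME class with the allocated threshold masked, and reveal the allocation only for the relatedness assessment. This guards the classification of submitted bleeds against knowledge of allocation. It does not recover unreported ones, which is why steps 1 and 2 come first.

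The cost is wording in a few subsections, a few more reports from sites, and some redaction of SAE reports before central review. Masking will be imperfect where the narrative shows whether platelets were given.

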9.3.2 Relatedness

- None: there is no evidence of any relationship to the trial treatment
- Unlikely: there is little evidence to suggest a relationship to the trial treatment, and there is another reasonable explanation of the event
- Possibly: there is some evidence to suggest a relationship to the trial treatment, although the influence of other factors may have contributed to the event
- Probably: there is probable evidence to suggest a relationship to the trial treatment, and the influence of other factors is unlikely
- Definitely: there is clear evidence to suggest a relationship to the trial treatment, and other possible contributing factors can be ruled out

9.3.3 Expectedness

- Expected: the event is a pre-defined expected SAE event for this trial.
- Unexpected: the event is not a pre-defined expected SAE event for this trial

Pre-defined expected SAEs for T4P that could be observed in participants up to ICU discharge following randomisation are:

- Major and fatal bleeds classified according to the HEME bleeding score
- Serious transfusion related adverse reactions which relate to the administration of the platelet transfusion

9.4 Recording and reporting procedures

Occurrences of the specified, expected Serious Adverse Events (SAEs) will be recorded and reported for all randomised patients from the time of randomisation until ICU discharge. If a patient is readmitted to the ICU during the index hospital stay within the 90 days, safety monitoring will be recommenced.

Considering that all eligible patients are critically ill and at increased risk of experiencing multiple adverse events due to the complexity and severity of their condition – occurrences of non-specified, unexpected, SAEs will only be reported if they are considered to have possibly, probably, or definitely (as per section 9.3.2) occurred as a consequence of receiving or not receiving a platelet transfusion for a low risk invasive procedure (i.e. not events that are part of the natural history of the primary disease process or expected complications of critical illness). Note that death itself should not be reported as an SAE, but the suspected cause of death should be assessed for severity, relatedness and expectedness as detailed above.

All SAEs (other than those defined in the protocol as not requiring reporting) must be recorded in the patients' medical notes and reported to the Australian and central (international) coordinating centre via completion of the SAE Report eCRF on the secure electronic data entry system, **within 24 hours** of observing or learning of the SAE(s). The completed SAE Report Form should be electronically signed off by the site PI (or medically qualified delegate). An email notifying the trial team of completion of the SAE Report Form should be sent to [contact] AND [contact]. Staff should not wait until all information about the event is available before sending SAE notification. Information not available at the time of the initial report must be documented and submitted as it becomes available. If the eCRF is unavailable, the SAE report can be completed on paper and a scanned copy sent by email to [contact] AND [contact].

On receipt of an SAE report, a member of the central (international) coordinating centre will first evaluate the report for completeness and internal consistency. Then, a clinical member of the central T4P Trial Management Group will evaluate the event for severity, relatedness and expectedness and liaise with the Australian Trial Management Group to determine whether the case qualifies for reporting to the (Australian) HREC and any further actions required, in accordance with local jurisdictional requirements and policy directives.

All other adverse events that occur between randomisation and 90 days post-randomisation (or ICU discharge, if sooner) must be recorded in the participant's medical notes.

The coordinating (international) centre will provide safety information to the DMEC on a basis deemed appropriate by the DMEC.

9.5 SUSARs

A SAE whose nature, severity, specificity, or outcome is not consistent with the expected complications of the intervention will be considered 'unexpected'. A SAE which is both unexpected and has a causal relationship with the study intervention will be reported as a Suspected Unexpected Serious Adverse Reaction (SUSAR) by the Australian Coordinating Centre to the TGA in an expediated fashion (i.e. within 15 calendar days of first knowledge), or for fatal or life-threatening events, an initial or full report within 7 calendar days and a follow-up report if necessary within the 15 calendar day timeframe. An investigator will complete, sign and submit the SUSAR report. These reports will then be forwarded to all sites for reporting to their HRECs as required.

9.6 Statutory reporting

All suspected transfusion reactions should also be reported as per local transfusion reaction reporting standard procedures.

10 Statistical and data analysis

10.1 Sample size

Sample size was estimated from simulations across 7 hypothesised threshold-response curves for the 90-day mortality primary outcome. These simulations are available in the simulations appendix at https://www.icnarc.org/Our-Research/Studies/Current-Studies/T4P/About. A sample size of 2400 resulted in power of at least 92% across the different scenarios to recommend an optimum threshold with a true mortality within 2% (in absolute value) of the optimum mortality value (Table 2, simulation appendix). The sample size was increased to 2550 patients to allow for 6% refusal/withdrawal of consent post-randomisation (as in the "65" Trial³⁶).

10.2 Australian sample size

An Australian sample size of 500 was chosen as this is a large enough cohort to complete an Australian economic evaluation and to increase the generalisability of the trial results to Australian patients. This figure is also feasible within the trial period and will coincide with the projected completion of recruitment in the UK (August 2027) and Australia within 3 years of Australian recruitment commencement.

Over a recent 12-month period at three tertiary and one regional ICU in South-East Queensland there were approximately 3.4 patients per site-month in the tertiary centres and 0.75 patients per month in the regional centre that met the inclusion criteria. Allowing for a recruitment rate of one in three eligible patients and a recruitment period of nearly three years, approximately 13 tertiary sized centres would be needed to recruit the target of 500 patients. To allow for smaller centres, a site ramp-up period of 6 months, and a lower than predicted recruitment rate, 20 Australian ICUs as Australian study sites will be recruited.

10.3 Clinical effectiveness analysis

All analyses will be pre-specified in a Statistical Analysis Plan published prior to the first interim analysis. Reporting will follow CONSORT guidance³⁷. Primary analyses will be on an intention-to-treat basis. Baseline patient characteristics will be compared across thresholds to assess the effectiveness of randomisation at achieving covariate balance.

The threshold-response curve for each outcome will be fitted using fractional polynomials of order 2 to estimate a continuous non-linear relationship between the allocated threshold and the outcome³⁸. Model uncertainty will be taken into account using Bayesian model averaging. The estimand of interest is the threshold leading to the maximum probability of survival. Binary outcomes (including the primary outcome) will be modelled using logistic regression, continuous outcomes using linear regression.

Regression models will be adjusted for stratification variables (random effect of site) and other prespecified patient factors with an established relationship with outcome among critically ill patients. These patient factors will be agreed with the Trial Steering Committee and prespecified in the Statistical Analysis Plan (SAP). As a sensitivity analysis for the primary outcome, the thresholdresponse curve will be fitted using a Gaussian process model.

The primary output will be a set of statistics derived from the estimated threshold response curve, including the location of the optimum, reported with a 95% credible interval and estimates of the probability of survival at all thresholds across the full range of investigated thresholds, each with a corresponding 95% credible interval. If the estimated threshold-survival curve is relatively flat (i.e. there are only small differences in mortality across the range) then the location of the optimum will

be less certain (i.e. have a wider credible interval) but any error in locating the optimum will also be less important. Both the shape of the curve and the location of the optimum are therefore of clinical interest. A steep curve would imply a narrow region within which clinical judgement should be exercised, and a flatter curve would support a wider region. Examples of potential outputs are provided in the simulation study report (see simulation results in the appendix found online https://www.icnarc.org/Our-Research/Studies/Current-studies/T4P/About).

Variation in the threshold-response curve shape and optimum threshold location in pre-defined patient subgroups will be evaluated by introducing interaction terms between the subgroups and the threshold in the threshold-response models for the primary outcome.

We will handle missing data appropriately within the Bayesian paradigm, adding imputation submodels for missing covariates if required. Assumptions about the missing values will be fully specified in the SAP.

Analyses of long-term outcomes involving data linkage to efficiently collect follow-up data are potentially subject to influence of linkage error (missed links between one patient's records or false links between different patients). With collection of multiple, highly specific patient identifiers (e.g. hospital number, postcode and date of birth), false links are expected to be negligible but will be assessed by checking linked records for implausible scenarios such as activity after death. Missed links due to incomplete or inaccurate recording of identifiers (especially in any of the linked datasets) are a common issue in studies of linked data and can lead to missing data and/or misclassification of outcomes. The risk of missed links will be minimised by collection of multiple patient identifiers, and match rates for linkage to core datasets across treatment groups. Where matching data are insufficient or where linkage has been unsuccessful to core datasets, all outcomes derived from linked data for that patient will be treated as missing.

